10.1.2. Recruitment Setting for WP3

Patients who have been approached to take part in MEDLEY WP1 will provide optional consent to take part in WP3 at the point of joining the study, or at the point of declining participation.

Qualitative and stakeholder components of the study will involve professionals working from other settings, particularly primary care (GPs). The aim will be to recruit GPs who have referred a patient who had registered to WP1 in the first instance, but this can be opened up to other GPs who have referred a patient meeting NG12 criteria for CXR outside of the study if required.

10.2. Eligibility Screening for WP1

Participating research sites will be required to complete a non-registration log of all patients who have been referred from general practice for CXR who fulfil the NG12 criteria and are considered potentially eligible for the study on the basis of their X-ray request but not recruited into the study. Documented reasons for ineligibility or declining participation will be collected and closely monitored by the CTRU as part of the regular review of recruitment progress. Non-registration logs should be returned to CTRU on a monthly basis. The following anonymised data will be collected on the non-registration log:

- Age
- Sex
- Index of multiple deprivation (according to participant's postcode)

- Ethnicity
- Date screened

Patients who are not registered either because they are ineligible or because they decline participation will also have the following recorded:

- Reason not eligible OR
- Reason declining participation
- Main language
- Whether or not the patient agrees to take part in WP3 including contact details and preferred method to receive further information

10.3. WP1 Informed Consent and Eligibility

The Principal Investigator (PI) retains overall responsibility for the informed consent of participants at their site and must ensure that any person delegated responsibility to participate in the informed consent process is duly authorised, trained and competent to participate according to the ethically approved protocol, principles of Good Clinical Practice (GCP) and Declaration of Helsinki 1996. The assessment of eligibility will be confirmed and the informed consent process will be undertaken by the PI or registered healthcare professional who is approved by the PI as detailed on the Authorised Personnel Log.

Informed consent must be obtained prior to the participant undergoing procedures that are specifically for the purposes of the study and are out-with standard routine care at the participating site including the collection of identifiable participant data. Participants must remain free to withdraw at any time from all or some aspects of the study without having to give reasons and without prejudicing their further treatment. Participants must be provided with a contact point where they may obtain further information about the study.

Where a participant is required to re-consent or new information is required to be provided to a participant it is the responsibility of the PI to ensure this is done in a timely manner and according to any timelines requested by the CTRU.

Informed consent can be taken either (i) face-to-face on a paper form (written consent), (ii) as remote e-consent using REDCap, (iii) as remote verbal consent over the telephone. The mode of informed consent used will depend on the patient preference. Consent can be provided on the same day as NICE guidance stipulates imaging should be undertaken urgently (within 14 days) and as many centres now offer 'walk-in' appointments, patients typically proceed to have their CXR within a day or two of their consultation in primary care. There is minimal risk to the participant from the additional LDCT. The burden for participants is also minimal as there are no in person follow ups, imaging can be completed on the same day (or within 7 working days of each other), and each investigation is expected to take no more than 15 minutes.

Patients who provide informed consent who subsequently permanently lose capacity will be withdrawn from the study. Data collected up until the point of CTRU becoming aware of loss of capacity will be used in the analysis.

Note: If the patient withdraws between consent and registration the original GP CXR request will remain active, the patient will be advised to attend for that investigation, the report would be returned to the GP for actioning, and the PI will have no responsibility for actioning the result.

Consent forms do not need to be returned to CTRU for patients who are not registered.

(i) written or witnessed verbal consent face-to-face

For participants who choose to complete in-person consent, a paper copy of the consent form will be completed with the researcher. Witnessed verbal consent may be used for patients who have capacity to consent but are unable to physically sign the paper form. Patients may prefer to speak to the researcher in person or may feel more comfortable asking questions about the study face-toface. The researcher may also feel this method is most appropriate after the initial telephone call, because of difficulties communicating over the telephone including language barriers or difficulty hearing. An in-person interpreter or telephone interpreting service could be used when completing consent this way.

(ii) remote e-consent using REDCap

Patients who choose to consent using remote eConsent will provide verbal consent for their initials, date of birth, email address and phone number to be disclosed to CTRU through the REDCap system. If the patient does not consent to this disclosure, they will be unable to use remote e-consent and a convenient time will be arranged to complete a remote verbal or paper consent process.

Assenting patients receive a link to a questionnaire (REDCap) prior to the eConsent telephone/video call. The researcher will discuss the study and what it involves, and each point on the consent form, with the patient. The patient will complete all questions and add a signature (by clicking a button to confirm completion of the form), then submit. The researcher will open the form and complete sign-off. The participant will receive an electronic copy of the consent form, or the researcher may download and post a copy if requested. Patients may prefer to receive things electronically, and not want to make the extra trip to hospital to see a researcher face-to-face. This process is efficient, and both the patient and researcher receive a completed copy within a short time frame. It also reduces paper resource use at the research site. If patients do not have access to, or feel confident using a computer and/or REDCap, face-to-face or verbal consent over the phone would be more appropriate. REDCap is also only available in English, which limits this form of consent.

(iii) remote verbal consent over the phone

For those not wishing to attend the hospital for face-to-face consent and unable to complete remote electronic consent (e.g. device accessibility) or preferring not to, the researcher will complete the consent form with the patient over the telephone. Each statement on the consent form will be read to the patient, with the researcher initialling and signing the consent form on behalf of the patient. A copy of the consent form signed on behalf of the patient will be posted/emailed to the patient. Patients may not have access to, or feel confident using a computer and/or REDCap but may also not want to make the extra trip to hospital to see a researcher face-to-face. Telephone interpreting service can be used when completing consent this way.

10.4. WP3 consent

10.4.1. Population

WP1 participants will be asked for optional consent to be contacted by a researcher about taking part in a qualitative interview at the point of entering until the target sample size has been reached. Participants will remain free to decline to take part in an interview at any time by revoking consent without giving reasons and without prejudicing further treatment. This includes withdrawing their data up to one week after the interview has taken place.

Patients who decline to participate in WP1 will also be offered the opportunity to take part in WP3, in order to understand reasons for non-participation. At the time of discussing participation for WP1 MEDLEY PROTOCOL V2.0 04/12/2024

patients who decline to participate will be asked if they may be contacted in the future regarding another part of the study. Patients who give this consent to be contacted again, despite having declined to participate in WP1, will be contacted and asked if they wish to consent to WP3.

Assenting patients will receive a WP3 information sheet via their preferred method (postal/email) and will be contacted by telephone to provide an opportunity to ask any questions and discuss the study details with the qualitative researcher. An interview time and date will be mutually agreed on, accommodating preferences for either a telephone or video interview. Verbal consent to be interviewed will be taken by the qualitative researcher at the start of the call using a separate verbal consent form and recorded. Recording will stop after verbal consent and restart for the formal interview.

10.4.2. GP and stakeholders

GPs who have referred patients will be contacted by a researcher about taking part in a qualitative interview. If the target sample size is not reached, other GPs who have not referred patients involved in the study will also be contacted through local Clinical Research Network contacts until the target sample size is reached. GPs will be free to decline to take part in an interview at any time without giving a reason.

GPs will be contacted via email with a WP3 participant information sheet attached. An interview time and date will be mutually agreed on, accommodating clinical priorities and preferences for either telephone or video interview. Verbal consent to be interviewed will be taken by the qualitative researcher at the start of the call using a separate verbal consent form and recorded. Recording will stop after verbal consent and restart for the formal interview.

We will compile a list of potential stakeholders, drawing on network contacts and key connections through the British Thoracic Oncology Society and the Roy Castle Lung Cancer Foundation. All stakeholders will be invited to our event via email with an information sheet. Potential participants will be able to ask questions via email or telephone prior to the event. Arrival at the event will indicate consent to participate.

10.5. WP1 Registration

Informed consent for entry into the study must be obtained prior to registration.

Following confirmation of informed consent and eligibility participants will be registered into the study by an authorised member of staff at the study research site. Registration will be performed centrally using the CTRU automated, secure, 24-hour registration system which can be accessed via the web. To register using the web-based system a staff site email address, site code and Personal Identification Number (PIN) will be required. Authorisation codes and PINs will be provided by the CTRU to access the registration service. These codes will only be issued once a site has been fully approved and all the necessary documentation has been received at CTRU.

The following information will be required at registration:

- Participant details, including initials, sex and date of birth
- Site code for research site
- Confirmation of eligibility
- Confirmation of written informed consent and date
- Confirmation of completion of the baseline questionnaire (where applicable paper/telephone administration only)

- Whether the participant requires an electronic link to complete the baseline questionnaire and preferred method of receipt and contact details (email/text) (where applicable)
- Preferred method of follow up questionnaire administration (where applicable electronic/postal/verbal)
- Decision regarding optional consent to be contacted for WP3 including phone number and preferred method to receive further information

Once registration is complete, the system will allocate a participant ID number which will be shown on screen.

After registration the research site will:

- Add the unique participant ID number to the consent form if completed on paper
- Return a copy of completed paper consent forms, contact details form and paper baseline questionnaires (where applicable) to CTRU via secure file transfer
- Send the GP letter notifying the participant's GP of their participation in the study
- Arrange the CXR and LDCT appointments for the participant, including creation of new CXR/LDCT requests under the named responsibility of the local PI.
- Cancel the GP CXR request. Note: Responsibility for actioning test results will transfer to the local PI at this point

11.0 Treatment/Intervention Details

Participants will receive LDCT (technology being assessed) in addition to current standard of care (which includes CXR). At the time of study registration, two new requests will be generated for LDCT and CXR by the local participating centre MEDLEY study team and the original CXR request (made by GP) will be cancelled by the MEDLEY study team. These will be requested under the name of the local Respiratory Physician PI, and that Respiratory team will take responsibility for reviewing and actioning results from the LDCT report and CXR report as per local standard of care practice.

11.1. LDCT

CT image acquisition protocol

Subject position:

Participants should lie supine on the CT table with arms above their head and thorax in the midline of the scanner. Subject comfort should be optimised, and maximal inspiration rehearsed prior to the scan to minimise motion during the CT. Imaging should be performed during suspended maximal inspiration. No intravenous contrast material will be administered.

Localiser:

Sites should use their standard scanogram scout view (scanogram) to localise the start and end positions of the scan. The frontal localiser should be performed in the PA projection and at the lowest possible setting to minimise breast dose.

Volumetric CT scan:

The lung parenchyma (lung apices to bases) must be scanned in its entirety in a single cranio-caudal acquisition. The field of view selected as the smallest diameter as measured from widest point of outer rib to outer rib large enough to accommodate the entire lung parenchyma. Thin detector collimation (≤1.25mm) will be used.

Exposure factors:

Radiation exposures will be as low as possible while maintaining good image quality. The acquisition parameters will be set to ensure that the calculated radiation dose delivered to each individual is below 2 mSv (based on the median standard 70kg adult). This will be done by ensuring that the kVp and mAs settings are varied according to participant body habitus. The height and weight of participants will be used to enable accurate selection of exposure factors. Medical physics input should be obtained when setting up LDCT scanning protocols, and a standardised protocol should be used.

11.2. CXR

A PA projection radiograph will be acquired at maximum inspiration according to local hospital protocols for adult patients.

11.3. Categorisation of image reporting

Imaging reports for all study LDCT and CXRs will be added to hospital records via the Radiology Information System (RIS) either automatically or through manual transfer of the report text. The reports will comprise a summary category (LDCT 1-6 and CXR 1-6) and free text report. Computeraided detection/artificial intelligence will not be used to analyse LDCT or CXR images.

- LDCT 1: Likely cancer for urgent review in clinic
- LDCT 2: Indeterminate finding requires follow-up CT (e.g. nodule)
- LDCT 3: Significant other respiratory finding requiring further clinical evaluation
- LDCT 4: Significant other non-respiratory finding requiring further clinical evaluation
- LDCT 5: No action required
- LDCT 6: Other
- CXR 1: Likely cancer urgent CT scan recommended
- CXR 2: Indeterminate finding requires follow-up chest X-ray (e.g. pneumonia)
- CXR 3: Non-malignant finding CT scan recommended (e.g. ILD)
- CXR 4: Non-malignant finding other investigation/clinical evaluation recommended (e.g. heart failure)
- CXR 5: No action required
- CXR 6: Other

The PI or delegated members of the team will review each imaging report for all registered participants at least weekly to action results. The LDCT result will primarily guide management, but the CXR report will also be reviewed in case of the rare scenario where an abnormality is noted on the CXR that is not seen on the LDCT (e.g. humeral lesion). If a participant has only completed one imaging modality, this will be used to guide management. A standardised letter will be sent to the GP, with a copy to the patient, (see section 12.8) including:

- a) What actions have been arranged in Secondary Care (maybe none)
- b) What actions are needed in Primary Care (maybe none)
- c) The full text of the LDCT report (for information) OR CXR report if LDCT not completed
- d) Comments from the clinical review meeting (maybe none)

11.4. Responsibility for further management

Actions required within secondary care (e.g. referral to the lung cancer service, referral to another hospital service, repeat imaging such as CT) will be arranged by the PI or delegated team as per local standard of care practice. Actions for Primary Care (e.g. antibiotics for a chest infection, repeat CXR MEDLEY PROTOCOL V2.0 04/12/2024

to ensure resolution of consolidation) will be clearly stated in section (b) of the letter. Coronary artery calcification, aortic valve calcification and emphysema will all be managed as per the hospital's normal policy for routine CT imaging. There is no requirement to follow the Targeted Lung Health Check protocol for these findings.

11.5. Withdrawal and opt-out

In the event a patient withdraws consent prior to registration, no further data is required to be submitted.

In the event a participant does not attend one or both of their imaging appointments they will continue to complete the follow up schedule unless unwilling to do so and eCRFs will continue to be collected unless consent for collection of follow up data is withdrawn.

Participants should not be withdrawn from the study unless it is harmful for them to continue, or the participant wishes to be withdrawn. The PI, or delegate should make every effort to ensure that the specific wishes of any participant who wishes to withdraw consent for further involvement in the study are defined and documented using the Early Study Completion CRF in order that the correct processes are followed by the CTRU and site.

Participants may 'opt out' of one, multiple or all of the components listed below.

- a) Completing a CXR
- b) Completing a LDCT
- c) Completing questionnaires
- d) Receiving phone calls
- e) Consent for their data to be used in future research
- f) Consent to be contacted to take part in qualitative interviews
- g) Collection of data from medical records

Participants who opt out of both components (a) and (b) i.e., non-attendance at both imaging appointments, will be contacted by telephone in the first instance to see whether it is feasible to rearrange an appointment within 14 days. If the participant is not contactable then a non-attendance letter will be sent to the participant and to the GP to inform them that no imaging has been performed (see below).

For participants who opt out of (a) the MEDLEY CXR request will be cancelled, the LDCT is outsourced for reporting as per protocol, and the PI will review the result and generate a standard MEDLEY output letter which will be sent to the participants' GP.

For participants who opt out of (b) the MEDLEY LDCT request will be cancelled, the CXR is outsourced for reporting as per protocol, the PI will review the result and generate a standard MEDLEY output letter which will be sent to the participants' GP.

In both of the above cases , clinical responsibility remains with the local PI.

For participants who opt out of components (a) - (f) (in any combination), data will continue to be collected as per the protocol schedule and all of the participants' data will be used in the analysis. Participants who opt out of all components (a) – (g) listed above will be considered a full study withdrawal, no further data will be collected past the point of withdrawal and data collected up to the point of withdrawal will be used in the analysis.

In line with the principles for handling end of participation events in clinical trials research (PeRSEVERE) (https://ukcrc-ctu.org.uk/page-persevere/), a letter will be posted/emailed to the participant, in the following circumstances;

- The participant does not attend either of their imaging appointments and it has not been possible to contact them by telephone.
 The letter will emphasise the importance of contacting their GP to arrange a new CXR appointment and provide contact details for more information or any questions.
- (ii) The participant has completed their imaging and subsequently opted out of one or more of (c) (g) above.
 The letter will thank them for their involvement in the study, confirm their position in the study going forward, offer the opportunity to follow progress and outcomes of the study and requesting feedback on their reasons for withdrawing if they are happy to do so.

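### Section 11.5 specifies a no-imaging letter to the GP when a participant who had neither test cannot be reached by telephone, but no GP notice when the participant is reached and still not imaged

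*Protocol*

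**What the plan says.** Section 10.5 lists the site's tasks after registration. One is "Cancel the GP CXR request". Another is a letter telling the participant's "GP of their participation in the study". Section 11.0 repeats the first: "the original CXR request (made by GP) will be cancelled by the MEDLEY study team". New requests for both tests are raised under the local principal investigator, who takes over acting on the results.

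Section 11.5 deals with missed tests. Someone who has neither is telephoned first, "to see whether it is feasible to rearrange an appointment within 14 days". The next sentence sets the trigger for the letter reporting that no imaging took place: "If the participant is not contactable then a non-attendance letter will be sent to the participant and to the GP". The list of participant letters later in 11.5 repeats the condition in item (i): "The participant does not attend either of their imaging appointments and it has not been possible to contact them by telephone".

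A participant who has one test but not the other is covered separately. The completed test is reported, and a standard output letter goes to the GP.

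**The concern.** Participants are symptomatic patients whose GP asked for an X-ray under NG12, and section 10.3 notes that such imaging should be done within 14 days. Once a participant is registered, the GP's own request no longer exists and the GP has been told that the patient is in the study. A GP in that position could reasonably assume that imaging is in hand.

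The protocol recognises the need for a safeguard in the neighbouring situations. If the patient withdraws between consent and registration, section 10.3 keeps the GP request active and has the patient advised to attend. If a registered participant cannot be reached, section 11.5 has the GP told that nothing was done. For a registered participant who is reached but still has neither test, there is no live GP request and no specified message to the GP. What is at stake is whether the referrer learns that the investigation did not happen. Sample size, the accuracy estimates and the analysis are unaffected.

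**Working it through.** No arithmetic applies. The check follows each branch open to a registered participant and asks which GP letter the text triggers.

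- **LDCT done, CXR not done:** standard output letter to the GP (11.5).
- **CXR done, LDCT not done:** standard output letter to the GP (11.5).
- **Neither done, not reachable:** non-attendance letter to participant and GP (11.5).
- **Neither done at first, reached, rebooked and imaged:** result letter (11.3, 12.8).
- **Neither done, reached, rebooked, misses again and is then unreachable:** the telephone-then-letter rule can be applied again, so the letter can follow.
- **Neither done, reached, and declines, cannot be rebooked or is still not imaged:** no GP notice specified.

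The same result follows from the three GP letters in the schedule of events (12.2), taken for the last branch:

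1. The baseline GP letter has already gone out at registration. Its described purpose is to notify participation, and it predates the missed tests.
2. The result letter follows review of a report. Section 11.3 lists among its contents "The full text of the LDCT report (for information) OR CXR report if LDCT not completed". With neither test there is no report.
3. The non-attendance letter is tied in 11.5 to failed telephone contact, which has not occurred.

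GP letters specified to report that no imaging was done in this branch: 0 of 3.

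Other provisions do not supply the step:

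- Participant letter (ii) in 11.5 applies to people who completed their imaging, so someone who withdraws by telephone before imaging fits neither (i) nor (ii).
- The wishes of a withdrawing participant are "documented using the Early Study Completion CRF in order that the correct processes are followed by the CTRU and site". The GP is not mentioned.
- The statement in 11.5 that clinical responsibility stays with the local principal investigator refers to the two single-test cases that precede it.
- Section 12.5 has attendance recorded within 2 working days and refers non-attendance at one or both appointments back to 11.5.
- Sections 12.2 and 12.6 mention a non-attendance letter without the telephone condition, but both qualify it as needed only where it applies.

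**The case against.** The strongest reply is that the protocol is silent here, not restrictive. Section 11.5 says what happens if contact fails; it does not say that the GP is told in that case alone, and nothing stops a site from informing the GP after a successful call. This stands. A reader might infer that the protocol withholds the information from the GP, but the text does not support that.

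A second reply is that 12.2 and 12.6 can be read more broadly. The 12.2 row names both patient and GP, and the 12.6 item concerns people who attended neither appointment; the qualifier on each could simply mean that neither test was attended. This is a fair reading and a site might adopt it. It does not settle the matter, because 12.5 makes 11.5 the governing process, the 12.6 entry is a data item that names no recipient, and 11.5 states a different condition. A reader might also call this a contradiction between sections; it is loose wording.

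Third, the letters themselves are not shown. The baseline letter may say more than that the patient has joined, and the non-attendance letter may already mention the cancelled request. That also stands, so nothing here rests on what those letters contain beyond the protocol's description.

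Fourth, the reached participant has had a live conversation about rebooking, which the unreachable one has not. It would therefore be wrong to say that this group is the least protected overall. The conversation informs the patient, however, and not the referrer whose request was cancelled.

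Lastly, a reader might infer that the study delays diagnosis. The documents do not show this. The patient may equally have refused the GP's X-ray, and the protocol does not say whether GPs are told of missed X-rays in usual care.

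**Conclusion.** The point holds as a narrow procedural gap. Section 11.5, followed as written, provides a GP notice when a participant with neither test cannot be reached, and none when the participant is reached and remains unimaged, although the GP's request was cancelled at registration.

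The conclusion rests on two readings: that 11.5 governs, as 12.5 indicates, and that the result letter needs a report, as 11.3 and 12.8 describe. It does not depend on any rate. The protocol gives no figure for non-attendance or telephone contact, so the number affected cannot be calculated; it is probably small. No estimate, confidence interval or progression criterion changes. This is a minor patient-safety correction, worth making because the remedy is cheap and the letter already exists.

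**What to change.** In section 11.5, including item (i) of the participant-letter list, replace the failed-contact trigger. Send the non-attendance letter to the GP, copied to the participant, for every registered participant who has completed neither test by the end of the 14-day rearrangement window, or at once if the participant declines both tests, whatever the outcome of the telephone call. State the date from which the 14 days run, so that sites know when the letter falls due.

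The letter should say three things: no imaging was done, the original GP request was cancelled, and a new request is needed if imaging is still wanted. Align the entries in 12.2 and 12.6 to this trigger, so that the qualifier there has one meaning.

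The cost is a few lines of protocol text, a check of the letter template, and a few extra letters, some to people who have already been spoken to.
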